6.9.1.6 Safety Parameters

Safety endpoints are:

- AEs
- ADRs
- Hypoglycaemic episodes
- Cardiovascular events
- laboratory measurements
- Vital signs (blood pressure, pulse rate and body temperature)
- 12-lead ECG

All safety summaries will be performed on the Safety Analysis Set. No formal statistical test would be performed to determine statistical significance between treatment groups.

6.9.2 Subgroup Analyses

Change in HbA1c from baseline to Week 24 will be analysed for the subgroup of baseline characteristics.

6.9.3 Interim Analyses

No interim analysis is planned.

6.9.4 Determination of Sample Size

[REDACTED]

7. Study Report and Publication Policy

Any formal presentation or publication of data from this trial will be considered by the appropriate sponsor personnel. For multi-centre studies it is mandatory that the first publication is based on data from all centres, analysed as stipulated in the protocol. Investigators agree not to present data gathered from one centre or a small group of centres before the full publication. In any case, the Sponsor will review any publications/communications/abstracts for accuracy (thus avoiding potential discrepancies with submissions to health authorities), verify that proprietary, confidential information is not being inadvertently divulged, and provide any relevant supplementary information.

8 References

[1] EMA 2012

Guideline on clinical investigation of medicinal products in the treatment or prevention of diabetes mellitus 14 May 2012 CPMP/EWP/1080/00 Rev. 1 Committee for Medicinal Products for Human Use (CHMP)

[2] ADA 2014

Diagnosis and Classification of Diabetes Mellitus. Diabetes Mellitus, Volume 36, Supplement 1, January 2014, S81-90

1 LIST OF ABBREVIATIONS AND DEFINITIONS OF TERMS

Table 1: Abbreviations and Definitions of Terms

ADR(s)	Adverse Drug Reaction(s)
AE(s)	Adverse Event(s)
ANCOVA	Analysis of Covariance
ATC	Anatomical Therapeutic Chemical
BDRM	Blinded Data Review Meeting
BMI	Body Mass Index
CFDA	China Food and Drug Administration
CI	Confidence Interval
CIP	Clinical Investigational Plan
CRF	Case Report Form
DPP-4	Dipeptidyl Peptidase-4
EAC	Event Adjudication Committee
ECG	Electrocardiogram
eCRF	Electronic Case Report Form
FAS	Full Analysis Set
FDA	Food and Drug Administration
FPG	Fasting Plasma Glucose
GGT	Gamma-Glutamyl Transferase
GIP	Glucose-dependent Insulinotropic Peptide
GLP-1	Glucagon Like Peptide-1
HbA1c	Glycosylated Fraction of Haemoglobin
HDL-C	High Density Lipoprotein Cholesterol
HR	Heart Rate
hr(s)	hour(s)
HOMA-β	Homeostatic Model Assessment-Beta
HOMA-IR	Homeostatic Model Assessment-Insulin Resistance
IB	Investigator's Brochure
IRB	Institutional Review Board
IWRS	Interactive Web Response System
Kg	Kilograms
LDH	Lactate Dehydrogenase
LDL-C	Low Density Lipoprotein Cholesterol
LOCF	Last Observation Carried Forward
LS-Mean	Least Square Mean
m	Metre
Max	Maximum
MedDRA	Medical Dictionary for Regulatory Activities
Mg	Milligram

Min	Minimum
MMRM	Mixed Model Repeated Measure
QTc	Q-T interval corrected for heart rate
N	Number of subjects
OR	Odds Ratio
RV	Randomization Visit
PPS	Per-Protocol Set
PT	Preferred Term
PV	Placebo Run-In Visit
SAE	Serious Adverse Event
SAP	Statistical Analysis Plan
SAS®	Statistical Analysis Software
SD	Standard Deviation
SE	Standard Error
SOC	System Organ Class
SV	Screening Visit
TEAE	Treatment Emergent Adverse Event
WHO	World Health Organization

2 INTRODUCTION

This Statistical Analyses Plan (SAP) describes the planned analyses to evaluate the efficacy and safety of MP-513 compared with placebo in Chinese subjects with type 2 diabetes mellitus inadequately controlled with diet and exercise.

The general information about the study is detailed in the MP-513-C02 protocol.

3 STUDY OBJECTIVES

[figure not shown]
The objective of this study is to evaluate the efficacy and safety of MP-513 compared with placebo in Chinese subjects with type 2 diabetes mellitus inadequately controlled with diet and exercise.

4 STUDY DESIGN

4.1 General Design

This is a multi-centre, randomized, double-blind, placebo-controlled, parallel-group study in subjects with type 2 diabetes mellitus.

The study flowchart is presented below:

4.2 Discussion of Study Design

The main characteristics of this study are:

- **Placebo run-in period:** The intention of the placebo run-in period is to exclude subjects who have poor treatment compliance, to enable a comparison of the effects of different treatments without the influence of placebo effect and to have a relatively stable HbA1c value at baseline.
- **Duration of double-blind treatment period:** HbA1c stabilizes over 24-week period. The double-blind treatment period is planned for 24 weeks to evaluate a stable HbA1c change from baseline compared with placebo and to investigate the safety/tolerability of MP-513 after treatment for this duration.
- **Dosage:** The dose of 20 mg orally administered once daily before breakfast is the established dose for this medication.
- **Safety Follow-up:** The two week safety follow-up period is sufficient to confirm the subjects' safety after the completion/discontinuation of the treatment.

4.3 Method of Assignment of Subjects to Treatment Groups

Treatment assignment will be managed through static blocked randomization and an Interactive Web Response System (IWRS) will be used.

After the Placebo run-in period, the eligible subjects will be randomized to one of the following treatment groups in a 1:1 allocation ratio:

- **Test Product:** One 20 mg tablet of MP-513, once daily before breakfast starting from the randomization visit (Day 1).
- **Placebo:** One placebo tablet, once daily before breakfast starting from the randomization visit (Day 1).

Randomization will be performed according to computer generated randomization scheme where a treatment group designation has been assigned to each subjects' randomization kit number. The treatment designation will remain blinded until the database is closed. An independent unblinded team within [REDACTED] will hold the randomization codes throughout the study, until authorization is provided by a Mitsubishi Tanabe Pharma Corporation representative to release the randomization schedule.

4.4 Blinding

Study treatments will be packaged for double-blind administration. The placebo is identical to the corresponding active treatments.

During single-blind run-in period, the subjects will not know that they are receiving placebo during the single-blind run-in period.

During the double-blind treatment period the subject, the investigator, the laboratory personnel, and the sponsor other than a designated person would not know the treatment arm to which a subject is assigned.

Unblinding of treatment for a subject may be performed in case investigator considers it necessary for the safety of the subject. The reason for breaking the blind along with date and time must be clearly documented in the source documentation and Case Report Form (CRF), and the subject will be discontinued from the study. The sponsor must be notified immediately upon all unblinding situations.

4.5 Determination of Sample Size

[REDACTED]

5 CHANGES IN THE CONDUCT OF THE STUDY OR PLANNED ANALYSES

5.1 Changes in the Conduct of the Study

This SAP is prepared based on the study protocol version 2.0 dated 29 April, 2016 and there are no planned changes either in the conduct of the study or planned analysis at the time of preparing this SAP.

6 BASELINE, EFFICACY AND SAFETY EVALUATIONS

6.1 Schedule of Evaluations

The assessments to be conducted at each scheduled visit are displayed in the below table.

Table 2 Schedule of Visits

Period	Scr. Period	Placebo Run-in Period		Double-Blind Treatment Period						Follow-up Period
		PV	RV	V1	V2	V3	V4	V5	V6	
Visit	SV	PV	RV	V1	V2	V3	V4	V5	V6	FV
Visiting Windows	Day -28 +/- 3 days	Day -14 +/- 3 days	Day 1	Week 4 +/- 7 days	Week 8 +/- 7 days	Week 12 +/- 7 days	Week 16 +/- 7 days	Week 20 +/- 7 days	Week 24 ⁽⁵⁾ +/- 7 days	Week 26 ⁽⁶⁾ + 14 days
Items										
Obtain written informed consent	X									
Screening/Inclusion/Exclusion criteria evaluation	X	X	X							
Demographics and complete medical history	X ⁽⁷⁾									
Height	X									
Body Weight	X		X	X	X	X	X	X	X	
Vital signs ⁽¹⁾	X	X	X	X	X	X	X	X	X	
12-lead ECG	X		X			X			X	
Routine laboratory evaluations: hematology, chemistry, urinalysis	X		X	X	X	X	X	X	X	
Serum pregnancy test ⁽²⁾	X								X	
HbA1c	X	X	X	X	X	X	X	X	X	
Fasting plasma glucose	X	X	X	X	X	X	X	X	X	
Fasting insulin, C-peptide and glucagon			X	X	X	X	X	X	X	
Dispense medication		X	X	X	X	X	X	X		
Return of unused medication			X	X	X	X	X	X	X	
Assessment of adverse events ⁽³⁾ and concomitant medication	X	X	X	X	X	X	X	X	X	X
Hypoglycaemic episodes ⁽⁴⁾	X	X	X	X	X	X	X	X	X	X
Dispense subjects diary and glucometer	X									
Subject diary review		X	X	X	X	X	X	X	X	

Scr period: Screening period, SV: Screening visit, PV: Placebo run-in visit, RV: Randomization visit, FV: follow-up visit

(1) Vital signs (sitting blood pressure, pulse rate and body temperature)

(2) The serum pregnancy test will be performed only for female subjects of childbearing potential.

(3) AEs will be collected and reported on the eCRF from the date of informed consent to 14 days after the final dose of the study drug considering the half-life (T1/2) of MP-513.

(4) The occurrence of hypoglycaemic episodes will be recorded continuously throughout the study by a subject diary

(5) These assessments will also be performed at early termination.

(6) Telephone visit

(7) Including physical examination

6.2 Time Point Algorithms

6.2.1 Study Day

The date of first dose of study drug administration during the double blind phase will be considered study day 1, and the day before the first dose of study drug of double blind phase will be study day -1. Study days will be calculated only when the full assessment date is known (i.e., partial dates will have missing study days).

$$\text{Study Day} = \begin{cases} \text{Date of Assessment} - \text{Date of Randomization Visit} + 1 \\ \text{For assessment on or after the day of randomization} \\ \\ \text{Date of Assessment} - \text{Date of Randomization Visit} \\ \text{For assessment before the day of randomization} \end{cases}$$

6.2.2 Windows

For the purpose of effectiveness and safety analysis, all scheduled and unscheduled clinic visits will be windowed as presented in the below table. The planned protocol visit window will be used for analysis.

Table 3 Schedule of Visits

Visit	Week	Scheduled Study Day	Visit Window in Protocol (Days)
Randomization Visit (RV)	Randomization Visit (RV)	1	1
Visit 1	Week 4	28	21 – 35
Visit 2	Week 8	56	49 – 63
Visit 3	Week 12	84	77 – 91
Visit 4	Week 16	112	105 – 119
Visit 5	Week 20	140	133 – 147
Visit 6	Week 24	168	161 – 175
Follow-up Visit	Week 26	182	182 – 196

If a visit day is outside of these windows, then it is considered as non-windowed, otherwise it is windowed. If a subject has more than one assessment occurring in the same visit window, the data from the visit closest to the scheduled study day will be used. If two visits have the same distance from the scheduled study day, the data of the visit after the scheduled study day will be used.

The unscheduled visits will be chronologically arranged between two scheduled visits. The unscheduled visits will be numbered sequentially with an increment of 0.1 to the visit number corresponding to scheduled visit preceding the unscheduled visit. For example, if two unscheduled visits occur between visit 1 (visit number is 10) and visit 2 (visit number is 20), then these unscheduled visits will be numbered 10.1, 10.2 in the order they occurred.

The assessments made in unscheduled visits will be considered in imputation of missing assessment using Last Observation Carry Forward (LOCF) method for Week 12 or Week 24.

6.3 Baseline Assessments

Baseline assessments will be the most recent assessment prior to the randomization.

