1.2. Protocol Synopsis

Sponsor: Mitsubishi Tanabe Pharma Corporation	Name of Medical Product: MP-513	Active Ingredient(s): Teneligliptin
Study Centre(s): Multi-centre study that will be conducted in approximately 35 sites in China		
Study Duration: 30 weeks (2 weeks screening, 2 weeks placebo run-in, 24 weeks treatment, 2 weeks follow-up) The study period is estimated to start from [REDACTED] to [REDACTED].		Study Phase: 3
Study Title: A phase 3 randomized, double-blind, placebo-controlled parallel group efficacy and safety monotherapy study of MP-513 in Chinese subjects with type 2 diabetes mellitus inadequately controlled with diet and exercise		
Study objectives: To evaluate the efficacy and safety of MP-513 compared with placebo in Chinese subjects with type 2 diabetes mellitus inadequately controlled with diet and exercise		
Methodology: Multi-centre, randomized, double-blind, placebo-controlled, parallel-group study		
Number of Subjects (Planned): 240 subjects (120 subjects to MP-513 and 120 subjects to placebo)		
Diagnosis and Inclusion Criteria: The subjects have to meet all of the following inclusion criteria: 
 1. A signed and dated informed consent form has been obtained from the subject, in accordance with International Conference on Harmonisation guidelines on Good Clinical Practice (ICH GCP), before any screening or study related procedures take place. 2. The subject is aged ≥ 18 years at signature of the informed consent form 3. Hospitalization status: outpatient 4. The subject has had a documented diagnosis of type 2 diabetes mellitus for at least 3 months at the screening visit (Day -28) 5. The subject is undergoing diet and exercise therapy, and diet and exercise regimen has not been changed for at least 8 consecutive weeks at the screening visit (Day -28). Subjects who cannot do exercise due to complication are not limited to this criteria. 6. The subject's glycosylated fraction of haemoglobin (HbA1c) is $\geq 7.0\%$ and $< 10.0\%$ at the screening visit (Day -28) and on Day -14. 7. The subject's fasting plasma glucose (FPG) is < 270 mg/dL (15 mmol/L) at the screening visit (Day -28) and on Day -14. 8. The subject is capable of giving informed consent, complying with the restrictions and requirements of the protocol and, in the opinion of the investigator, will be able to complete the study. 		

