Once a suitable candidate is identified from among the outpatients coming to the site for the scheduled visit, the investigator or designated healthcare professional will ask the subject about their willingness to be included in the clinical trial. The subject is to be informed verbally and in writing about the nature, risks, benefits, and expectations of participating in the clinical trial and a copy of the subject informed consent form is to be given to the subject in the appropriate language. The subject informed consent form is to be signed by the subject and countersigned by the attending investigator prior to proceeding with the visit. At this point, a subject screening number is to be assigned.

The investigator will provide subjects with a subject diary and glucometer, and will instruct them when and how to write in the subject diary and also when and how to monitor their own blood glucose by glucometer. The subjects should write in the subject diary and should monitor their blood glucose by glucometer as much as possible when hypoglycaemia occurs. The subjects should visit the investigator promptly when the hypoglycaemia is not recovered by the treatment such as taking glucose.

The following observations/procedures are to be performed and checked:

- Check inclusion/exclusion criteria
- Obtain written informed consent
- Complete physical examination including body weight, height, vital signs and ECG
- Complete demographic data and medical history
- Review use of previous/concomitant treatments
- Conduct a pregnancy test for female subjects of childbearing potential at the screening visit. Female subjects of childbearing potential have to confirm that they are using approved means of contraception. Menopause and hysterectomy and/or oophorectomy are to be documented.
- Blood and urine is to be drawn and sent to the central laboratory according to the local procedure for evaluation of haematology, clinical chemistry, urinalysis, HbA1c, and FPG.
- Subjects will be instructed to return for the placebo run-in visit 2 weeks later.
- Dispense of subject diary and glucometer.

Placebo Run-in Visit (14 days plus/minus 3 days prior to treatment)

The following observations/procedures are to be performed and checked:

- Check inclusion/exclusion criteria
- Review of subject's clinical charts, results of laboratory examination and blood pressure to confirm entry criteria
- Vital signs

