- Blood is to be drawn and sent to the central laboratory* according to the local procedure for evaluation of HbA1c and FPG evaluation.
- Evaluation for any AEs including hypoglycaemic episodes experienced by the subjects since last visit
- Subjects receive single-blinded placebo to take once daily. This will be dispensed to the subjects. Subjects should start administration of placebo from the placebo run-in visit.
- Review subject diary
- Subjects are to be instructed that they have to return for the next scheduled visit day.

* When the investigator considers there are proper reasons, it is allowed to evaluate HbA1c and FPG at each study site.

Randomization Visit (1 day of treatment)

The following observations/procedures are to be performed and checked:

- Check inclusion/exclusion criteria
- Review of subject's clinical charts, results of laboratory examination and blood pressure to confirm entry criteria
- Vital signs, body weight and ECG
- Review use of concomitant treatments
- Blood and urine is to be drawn and sent to the central laboratory according to the local procedure for evaluation of haematology, clinical chemistry, urinalysis, HbA1c, FPG, fasting insulin, C-peptide and glucagon
- Evaluation for any AEs including hypoglycaemic episodes experienced by the subjects since last visit

-
- Review subject diary
 - Randomization to MP-513 or placebo. This will be dispensed to the subjects. Unused placebo from the placebo run-in period has to be returned to the site. Investigator calculates the drug compliance of the placebo run-in period and confirms whether the subject doesn't meet the exclusion criteria #18. Subjects should start administration of MP-513 or placebo from the randomization visit.
 - Subjects are to be instructed that they have to return for the next scheduled visit day.

Treatment Visit 1 (Week 4 plus/minus 7 days of treatment)

The following observations/procedures are to be performed and checked:

- Vital signs, body weight
- Review use of concomitant treatments
- Blood and urine is to be drawn and sent to the central laboratory according to the local procedure for evaluation of haematology, clinical chemistry, urinalysis, HbA1c, FPG, fasting insulin, C-peptide and glucagon
- Evaluation for any AEs including hypoglycaemic episodes experienced by the subjects since last visit
- Review subject diary
- MP-513 or placebo will be dispensed to the subjects. Unused medication has to be returned to the site.

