7.2 Adjustments for Covariates

The efficacy variable being analysed will be adjusted for its baseline value, as a covariate in the model.

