8.7.2 Analysis of Secondary Efficacy Variables

All analysis on secondary efficacy variables will be performed using FAS.

The secondary efficacy endpoint is to evaluate the change in FPG from baseline to week 24 of MP-513 compared to Placebo. The same statistical methodology as described for primary analysis on primary efficacy endpoint will be used.

The line graph for mean change in FPG from baseline to Week 24 and Week 24 (LOCF) will be presented. The 95% CIs will also be shown in the graph with error bar. The plots of Week 24 and Week 24 (LOCF) will not be connected.

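### FPG is measured three times before treatment, but its analysis adjusts for one value only, giving up some precision on the sole secondary endpoint

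*SAP*

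**What the plan says.** Protocol 6.6.1 (Table 2 and the visit descriptions) and SAP 6.1 schedule FPG at three visits before double-blind treatment:

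- Screening, Day -28: central-laboratory "evaluation of haematology, clinical chemistry, urinalysis, HbA1c, and FPG".
- Placebo run-in visit, Day -14: a central sample "according to the local procedure for evaluation of HbA1c and FPG evaluation". A footnote adds that, where the investigator sees proper reason, "it is allowed to evaluate HbA1c and FPG at each study site".
- Randomization visit, Day 1: central-laboratory "evaluation of haematology, clinical chemistry, urinalysis, HbA1c, FPG, fasting insulin, C-peptide and glucagon".

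Inclusion criterion 7 makes the first two values compulsory: "fasting plasma glucose (FPG) is < 270 mg/dL (15 mmol/L) at the screening visit (Day -28) and on Day -14".

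The SAP carries one value forward. Section 6.3: "Baseline assessments will be the most recent assessment prior to the randomization". Section 7.2: "The efficacy variable being analysed will be adjusted for its baseline value, as a covariate in the model". Section 8.7.2, for FPG: "The same statistical methodology as described for primary analysis on primary efficacy endpoint will be used". That methodology (SAP 8.7.1.1) is an ANCOVA with treatment and a single baseline, and the Appendix 11.1.1 code has one `base` term. The protocol synopsis and Protocol 6.9.1.5 specify the same model. The two earlier FPG values serve eligibility and enter no efficacy model.

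**The concern.** A single fasting glucose varies from day to day, so it is a noisy measure of a subject's usual level. ANCOVA on one noisy value removes less between-subject variance than ANCOVA on several. Conditions suit the use of all three values: no anti-diabetic drug from 8 weeks before screening, diet and exercise unchanged, and only placebo given before Day 1. Every eligible randomised subject should already have both earlier values.

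What is at stake is the width of the confidence interval for the FPG difference at Week 24. Adding a pre-treatment covariate leaves the treatment difference being estimated, the sample and the endpoint definition as they are.

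**Working it through.** **What can be reproduced.** The documents state no precision or power figure for FPG, and the sample-size sections are redacted, so there is no plan figure to reproduce. From the documents: 120 subjects per arm, three pre-treatment FPG values, one used. All variances and correlations below are assumptions.

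**Model.** Each pre-treatment value is a stable level (SD b) plus independent visit noise (SD w). Week 24 is slope s times the stable level, plus drift (SD d), plus visit noise.

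- Total variance at Week 24: s²b² + d² + w²
- Residual, Day 1 only: total − s²b⁴/(b² + w²)
- Residual, all three values: total − s²b⁴/(b² + w²/3)

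Under this model, Day 1 plus the mean of the two earlier values, with free coefficients, achieves the three-value residual.

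**One case in full** (b = 30, w = 15, d = 22.5, s = 0.7):

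- Total: 441 + 506.25 + 225 = 1172.25
- Day 1 only: 1172.25 − 396,900/1125 = 1172.25 − 352.80 = 819.45
- All three: 1172.25 − 396,900/975 = 1172.25 − 407.08 = 765.17
- Ratio 765.17/819.45 = 0.934, a 6.6% cut in variance. √0.934 = 0.966, so the interval is about 3.4% narrower.
- Day 1 plus Day -28 only (Day -14 measured locally): 1172.25 − 396,900/1012.5 = 780.25, a 4.8% cut.

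**Range** over b = 25, 30, 35; w = 10, 15, 20; d = 15, 22.5, 30 (27 combinations per slope, no truncation):

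| Slope | Variance cut, range | Median | CI narrower at median |
|---|---|---|---|
| 1.0 | 5.0-19.6% | 11.7% | 6.0% |
| 0.7 | 2.6-11.5% | 6.4% | about 3% |
| 0.5 | 1.3-6.5% | 3.5% | 1.8% |

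The 19.6% maximum (b = 35, w = 20, d = 15, s = 1.0) has a baseline-to-Week-24 correlation of 0.71.

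**Cross-check by correlations.** Let rb be the correlation among pre-treatment values and rp that between a pre-treatment value and Week 24. The residual is 1 − rp² with one value and 1 − 3rp²/(1 + 2rb) with three. At rp = 0.5:

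- rb = 0.8: 0.712/0.750 = 0.949, like 240/0.949 = 253 subjects under the current analysis
- rb = 0.7: 0.688/0.750 = 0.917, like 262
- rb = 0.6: 0.659/0.750 = 0.879, like 273

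A comparison with 80% power would rise to about 82%, 83% and 85% respectively.

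**Robustness.** Simulating the entry limit of 270 mg/dL (assumed mean 170, SD 40, rb = 0.7, rp = 0.5) gives 0.918 against 0.917 without it. With serially correlated levels plus noise (single-value reliability 0.6-0.9), ratios are 0.90-0.99. The gain is zero if FPG follows a noise-free first-order process.

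**A version to avoid.** Replacing the Day 1 covariate with the three-value mean, while still analysing change from Day 1, raises the variance: ratios of 1.07-1.22 under the assumed correlations.

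**HbA1c, optional.** The same correlation formula gives these cuts: 2.4% (rb 0.90, rp 0.5), 4.0% (0.90, 0.6), 1.1% (0.95, 0.5) and 1.9% (0.95, 0.6).

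**The case against.** The planned model is standard, unbiased and consistent with the protocol. No FPG effect size or SD is available, so nothing shows that precision on FPG is limiting or that a conclusion would change. All of that stands, and it makes this an improvement rather than a correction.

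The size is also uncertain. It depends heavily on the slope: at 0.5 every combination gives less than 8%. The calculation leaves out LOCF at Week 24, discontinuation on the FPG thresholds in Protocol 6.3.3, HbA1c selection at the two earlier visits, and any placebo effect during the run-in that would make the three values less exchangeable. Their net effect on the gain is unknown. Local measurement at Day -14 would lose part of the gain, and the documents do not say how often it will occur. These points limit the size. They do not reverse the direction, because an additional pre-treatment covariate cannot raise the large-sample residual variance.

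A reader might infer that the FPG analysis is biased or underpowered, or that a gain near the top of the range can be expected. The documents support none of these. The single-value ANCOVA is valid, no power figure for FPG is given, and cuts approaching 20% need a slope near 1 and a high baseline-to-Week-24 correlation.

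**Conclusion.** The point holds as a missed efficiency on the only secondary endpoint. Three pre-treatment FPG values are planned and one is used. Under the assumed SDs and slopes of 0.5-1.0, residual variance would fall by about 1-20%, with medians of about 3-12% depending on slope, so the confidence interval would be roughly 2-6% narrower at the medians. For HbA1c the gain is about 1-4% of variance, at assumed pre-treatment correlations of 0.90-0.95 and baseline-to-Week-24 correlations of 0.5-0.6. That makes it an optional extension only.

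**What to change.** Before unblinding:

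- Keep Day 1 FPG as the reference for change and as a covariate.
- In SAP 7.2 and 8.7.2, add the mean of the central-laboratory Day -28 and Day -14 FPG values as a second covariate. Use Day -28 alone where Day -14 was measured at the site.
- State that the Day 1 covariate is not to be replaced by a three-value mean.
- Add the term to the Appendix 11.1.1 code for the FPG analysis.
- Declare the change in SAP section 5, since it departs from the model in the protocol synopsis and Protocol 6.9.1.5, and SAP 5.1 currently states that there are no changes to the planned analysis.
- Optionally, do the same for HbA1c.

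The cost is one degree of freedom and the declared SAP change. No new sample or visit is needed.
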